Studies have demonstrated that inhibition of the Hh pathway in embryos results in brain, facial, and other midline defects, including holoprosencephaly or microencephaly, cyclopia, absent nose, cleft palate, tooth abnormalities, and bone development abnormalities ([Bale, 2002](#)). While the teratogenic potential of GDC-0449 has not been investigated, given the key role of the Hh pathway in embryogenesis and the known teratogenic effects of cyclopamine, a naturally occurring inhibitor of SMO, women who are pregnant or nursing are excluded from all studies. Furthermore, to prevent pregnancy and the risk of fetal exposure to GDC-0449, women should not become pregnant during the GDC-0449 treatment or up to 12 months following cessation of therapy. Pregnancy prevention measures should be taken for all women of childbearing age for the study duration and for 12 months after the last treatment dose (refer to [Appendix C](#) for appropriate pregnancy prevention measures). In addition, it is not known whether GDC-0449 present in seminal fluid would cause teratogenic effects in the fetus born to the female partner of a male subject. Therefore, all sexually active male subjects should utilize a form of barrier contraception (even if they have a vasectomy) during study treatment and for 12 months following administration of the last dose.

As nonclinical studies have demonstrated a risk of teratogenicity following oral Hh pathway antagonists both pre- and post-natal, special care should be taken in pediatric populations. Specifically, GDC-0449 may adversely affect the development and maintenance of teeth, bones, and growth plates in a pediatric population.

Clinical Pharmacokinetics and Pharmacodynamics

Pharmacokinetic and Pharmacodynamic Analyses are fully available from the 33 basal-cell carcinoma patients. The median maximal plasma level was 23.0 μM (interquartile range, 16.8 to 29.7). The median steady-state concentration was 16.1 μM (interquartile range, 13.7 to 21.6). The median time to steady state was 14 days (interquartile range, 7 to 22). Increasing the dose from 150 mg to 270 mg did not result in higher steady-state plasma levels, with a median steady-state level of 19.8 μM (interquartile range, 13.5 to 25.8) for the 150-mg dose and 15.9 μM (interquartile range, 13.8 to 17.7) for the 270-mg dose. A consistent steady-state total plasma level of GDC-0449 was maintained throughout the treatment period, with no apparent decline at the time of disease progression. Pharmacodynamic down-modulation in the hedgehog pathway was shown by a decrease in *GLI1* expression by more than a factor of two, as compared with pretreatment biopsy-sample analysis, in 10 of 13 patients. The extent of *GLI1* down-modulation did not correlate with pharmacokinetic levels of GDC-0449 in individual patients.

Pharmacokinetic Analysis and Molecular Correlates of GDC-0449 Administration in 33 patients with basal-cell carcinoma.

Panel A shows the pharmacokinetic analysis of GDC-0449 for each of the 33 enrolled patients, according to dose. Three patients were exposed to a single dose on day 0, followed by repeated daily administration of GDC-0449, starting on day 7. The remaining 30 patients received daily doses, starting on day 0. Panel B shows mean concentration–time data for 30 patients who received either 150 mg or 270 mg of GDC-0449. The vertical lines represent standard deviations. Panel C shows elevated *GLII* messenger RNA (mRNA) expression in archival tissue obtained from 25 of 26 patients with metastatic or locally advanced basal-cell carcinoma (BCC), as compared with control specimens. *GLII* expression levels were assessed with the use of real-time polymerase-chain-reaction assay and calculated by the $2^{-\Delta Ct}$ method, in which the cycling threshold (Ct) of *GLII* was normalized to the Ct of *SMO* and expressed as a power of 2 ($2^{Ct(GLII)-Ct(SMO)}$). The mean ($2^{\text{Mean}(-\Delta Ct)}$) and standard deviation ($2^{\text{SD}(-\Delta Ct)}$) are indicated below the chart for each tissue type. Data for control subjects with either normal or malignant lung samples are included, since some specimens of metastatic basal-cell carcinoma represented lung metastases.

In vitro studies have indicated that GDC-0449 inhibits CYP2C8, CYP2C9, and CYP2C19 at clinically relevant concentrations. Care should be taken in administration of GDC-0449 with concurrent medications that are substrates of CYP2C8, CYP2C9, and CYP2C19 and have narrow therapeutic windows ([see Section 5.2.1](#) for a list of relevant medications). Of note, GDC-0449 did not inhibit CYP3A4 at clinically relevant concentrations; however, GDC-0449 is a substrate of CYP3A4. Effects of CYP inducers and strong inhibitors of CYP3A4 on GDC-0449 clinical concentration are not known; thus, use of these drugs should be carefully documented.

Proposed dose for GDC-0449

Based on the PK parameters and the lack of AEs observed, the proposed starting dose for oral administration of GDC-0449 to cancer patients is 150 mg/day (92.5 mg/m²/day).

2.3 Rationale

A way to try to improve the outcome of patients with sarcomas is to use the increasing amount of data about the biology of each tumor subtype to develop successful tailored systemic therapies ([Wunder et al., 2007](#)). This strategy has proven successful for imatinib-treated patients with GIST.

Chondrosarcomas exhibit a strong activation of hedgehog signaling which play a crucial role in cartilage tumorigenesis by maintaining tumor cells in a proliferative state. *In vitro* experiments have shown that treatment of chondrosarcoma cells with recombinant Hedgehog increased proliferation. Moreover, preclinical data from human chondrosarcomas explant and xenograft studies show that hedgehog blockade reduces strongly cell proliferation and tumour size ([Tiet et al., 2006](#)). We hypothesize that drug GDC-0449 is an agent of choice for patients with advanced chondrosarcomas by interfering with the hedgehog signaling pathway.

2.4 Correlative Studies Background

The presence of an activated and functional hedgehog pathway (expected in the majority of patients with chondrosarcomas) will be assessed for each case included in the clinical study. The expression pattern of hedgehog signaling molecules (Shh, PTCH, Smo, Gli-1, Gli-2, Gli-3) will be analyzed by using quantitative reverse transcription-polymerase chain reaction and

immunohistochemistry (IHC). The mutational status of *PTCH* and *SMO* will be also investigated immunohistochemistry methods. The 6-months clinical benefit rate will be correlated with the mutational status of *PTCH* and *SMO* and with the expression score of hedgehog signaling molecules (Shh, *PTCH*, *Smo*, *Gli-1*, *Gli-2*, *Gli-3*).

3. PATIENT SELECTION

3.1 Eligibility Criteria

- 3.1.1 Patients must have histologically confirmed diagnosis of chondrosarcoma (conventional, mesenchymal, dedifferentiated or clear cell subtypes).
- 3.1.2 Patients must have measurable disease (outside any previously irradiated field) defined as at least one lesion that can be accurately measured in at least one dimension (longest diameter to be recorded) as ≥ 10 mm with spiral CT scan. [See Section 11](#) for the evaluation of measurable disease.
- 3.1.3 No more than three prior lines of chemotherapy for advanced disease (including no more than 450 mg/m² doxorubicin). At least three weeks since last chemotherapy (six weeks in case of nitrosoureas and mitomycin C), immunotherapy or any other pharmacological treatment and/or radiotherapy.
- 3.1.4 Age ≥ 18 years (Because only limited adverse event data are currently available on the use of GCD-0449 in patients < 18 years of age, children are excluded from this study but will be eligible for future pediatric phase 2 combination trials).
- 3.1.5 Life expectancy of greater than 3 months
- 3.1.6 ECOG performance status ≤ 2 (Karnofsky $\geq 60\%$; see [Appendix A](#)).
- 3.1.7 Patients must have normal organ and marrow function as defined below:
 - a. leukocytes $\geq 3,000/\text{mcL}$
 - b. absolute neutrophil count $\geq 1,500/\text{mcL}$
 - c. platelets $\geq 100,000/\text{mcL}$
 - d. total bilirubin within normal institutional limits
 - e. AST(SGOT)/ALT(SGPT) ≤ 2.5 X institutional upper limit of normal
 - f. Creatinine within normal institutional limitsOR
creatinine clearance > 60 mL/min/1.73 m² for patients with creatinine levels above institutional normal
- 3.1.8 Metastatic or unresectable locally advanced disease.
- 3.1.9 Documented disease progression (as per RECIST) before study entry.
- 3.1.10 Hh pathway inhibitors such as vismodegib have been demonstrated to be embryotoxic and/or teratogenic in multiple animal species and can cause severe midline defects, missing digits, and other irreversible malformations in the developing embryo or fetus. For this reason, women of child-bearing potential and men must use two forms of contraception (i.e., barrier contraception and one other method of contraception) at least 4 weeks prior to study entry, for the duration of

study participation, and for at least 24 months post-treatment for female patients and for 2 months for male patients. For appropriate methods of contraception considered acceptable [see Appendix C](#). Should a woman become pregnant or suspect she is pregnant while participating in this study, she should inform her treating physician immediately.

- 3.1.11 **Pregnancy Testing.** Women of childbearing potential are required to have a negative serum pregnancy test (with a sensitivity of at least 25 mIU/mL) within 7 days prior to initiation of GDC-0449 treatment (serum or urine). A pregnancy test (serum or urine) will be administered every 4 weeks while on study within the 24-hour period prior to the administration of GDC-0449. A positive urine test must be confirmed by a serum pregnancy test. Prior to dispensing GDC-0449, the investigator must confirm and document the patient's use of two contraceptive methods, dates of negative pregnancy test, and confirm the patient's understanding of the teratogenic potential of GDC-0449.

Women of childbearing potential are defined as follows:

- Patients with regular menses
- Patients with amenorrhea, irregular cycles, or using a contraceptive method that precludes withdrawal bleeding
- Women who have had a tubal ligation

Women are considered not to be of childbearing potential for the following reasons:

- The patient has undergone hysterectomy and/or bilateral oophorectomy.
- The patient is post-menopausal defined by amenorrhea for at least 1 year in a woman > 50 years old.
- The patient has permanent premature ovarian failure confirmed by specialist gynecologist

- 3.1.11 Ability to understand and the willingness to sign a written informed consent document.

- 3.1.12 In accordance with French Regulatory Authorities: Patients with French Social Security in compliance with the French law relating to biomedical research (Huriet Law 88-1138 and related decrees).

3.2 Exclusion Criteria

- 3.2.1 Patients who have had chemotherapy or radiotherapy within 3 weeks (6 weeks for nitrosoureas or mitomycin C) prior to entering the study or those who have not recovered from adverse events due to agents administered more than 3 weeks earlier.
- 3.2.2 Patients may not be receiving any other investigational agents.

- 3.2.3 Patients with known brain metastases should be excluded from this clinical trial because of their poor prognosis and because they often develop progressive neurologic dysfunction that would confound the evaluation of neurologic and other adverse events.
- 3.2.4 History of allergic reactions attributed to compounds of similar chemical or biologic composition to GDC-0449 or other agents used in the study.
- 3.2.5 Patients with malabsorption syndrome or other condition that would interfere with intestinal absorption. Patients must be able to swallow capsules.
- 3.2.6 Patients with clinically important history of liver disease, including viral or other hepatitis or cirrhosis are ineligible.
- 3.2.7 Patients with uncontrolled hypocalcemia, hypomagnesemia, hyponatremia or hypokalemia defined as less than the lower limit of normal for the institution, despite adequate electrolyte supplementation are excluded from this study.
- 3.2.8 Tumor tissue sample not available for pathological review and/or correlative studies.
- 3.2.9 Uncontrolled intercurrent illness including, but not limited to, ongoing or active infection, symptomatic congestive heart failure, unstable angina pectoris, cardiac arrhythmia, or psychiatric illness/social situations that would limit compliance with study requirements.
- 3.2.10 Pregnant women are excluded from this study because GDC-0449 is a Hh pathway inhibiting agent with the potential for teratogenic or abortifacient effects. Because there is an unknown but potential risk for adverse events in nursing infants secondary to treatment of the mother with GDC-0449, breastfeeding should be discontinued if the mother is treated with GDC-0449. These potential risks may also apply to other agents used in this study.
- 3.2.11 HIV-positive patients on combination antiretroviral therapy are ineligible because of the potential for pharmacokinetic interactions with GDC-0449. In addition, these patients are at increased risk of lethal infections when treated with marrow-suppressive therapy. Appropriate studies will be undertaken in patients receiving combination antiretroviral therapy when indicated.

3.3 Inclusion of Women and Minorities

Both men and women and members of all races and ethnic groups are eligible for this trial. In accordance with French Regulatory Authorities, no data related to ethnicity will be collected.

4. REGISTRATION PROCEDURES

4.1. General Guidelines

Eligible patients will be entered on study centrally at the Institut Bergonié Coordinating Center by the Study Coordinator. All sites should call the Responsive Clinical Research Assistant ([contact]) to verify agent availability. The required forms can be found in [Appendix F](#)

Following registration, patients should begin protocol treatment within 72 hours. Issues that would cause treatment delays should be discussed with the Principal Investigator. If a patient does not receive protocol therapy following registration, the patient's registration on the study may be canceled. The Study Coordinator should be notified of cancellations as soon as possible.

Each participating institution will order GDC-0449 directly to the Pharmacy of Institut Bergonie.

4.2. Registration Process

To register a patient, **the following documents should be faxed** to the Bergonié Institute Data Center:

Clinical Trial and Epidemiology Unit – Institut Bergonié
[contact]
From Monday through Friday - From 9.00 am to 5.00 pm
Contact : [name] (CRA) - Tel : [name] , Mail – [contact]

This must be done **before the start of the protocol treatment which should begin within 72 hours following registration.**

The following documents should be completed and faxed by the clinical research assistant or data manager:

- Copy of required laboratory test
- Anonymized signed patient consent form (2 letters/NAME ; 2 letters/SURNAME)
- Registration form ([Appendix F](#)):
 - Institution number
 - Name of the responsible investigator
 - Patient's code (2 letters of name, 2 letters of first name)
 - Patient's birth date (day/month/year)
 - Eligibility criteria
 - Data foreseen for protocol treatment start

The clinical research assistant or data manager at the participating site will then call the Bergonié Institute Data Center to verify eligibility.

To complete the registration process, the Coordinator will:

- Assign a patient study number
- Register the patient on the study
- Fax or e-mail the patient study number
- Call the research nurse or data manager at the participating site and verbally confirm registration

The patient study number attributed at the end of the registration procedure identifies the patient and must be reported on all case report forms.

Issues that would cause treatment delays should be discussed with the Principal Investigator. If a patient does not receive protocol therapy following registration, the patient’s registration on the study may be cancelled. The Study Coordinator should be notified of cancellations as soon as possible.

5. TREATMENT PLAN

5.1 Agent Administration

Treatment will be administered on an outpatient basis. Reported adverse events and potential risks for GDC-0449 are described in [Section 7](#). Appropriate dose modifications for GDC-0449 are described in [Section 6](#). No investigational or commercial agents or therapies other than those described below may be administered with the intent to treat the patient's malignancy.

| REGIMEN DESCRIPTION | | | | | |
|----------------------------|--|-------------|--------------|-----------------|---------------------|
| Agent | Premedications; Precautions | Dose | Route | Schedule | Cycle Length |
| GDC-0449 | Take with or without food at the same time every day | 150 mg | PO | Days 1-28 | 4 weeks (28 days) |

5.1.1 GDC-0449

- GDC-0449 is an oral drug. Patients should take GDC-0449 at approximately the same time every day, with or without food. Capsules should not be opened. If a patient misses a dose, he or she should be instructed not to take or make up that dose and to resume dosing with the next scheduled dose. Missed doses should not be made up. Patients will be instructed to bring all unused capsules and their medication diary (refer to [Appendix E](#)) to each study visit for assessment of compliance.
- Patients should be warned not to share their supply of GDC-0449.
- Investigators may dispense no more than a 32-day supply of GDC-0449.

5.2 General Concomitant Medication and Supportive Care Guidelines

5.2.1 GDC-0449

- Clinically significant PK interactions between vismodegib and CYP450 inhibitors are not expected.
- Inducers of CYP3A4 are not predicted to alter vismodegib systemic exposure
- Drugs that Inhibit Drug Transport Systems : Clinically significant PK interactions between vismodegib and P-gp inhibitors are not expected
- Drugs that Affect Gastric pH : Clinically significant PK interactions between vismodegib and pH elevating agents are not expected.

- Effects of Vismodegib on Other Drugs : Clinically significant PK interactions between vismodegib and CYP450 substrates are not expected. Inhibition of CYP enzymes by vismodegib may be excluded.
- No clinically significant PK interaction between vismodegib and the oral contraceptives ethinyl estradiol and norethindrone.
- Clinically significant PK interactions between vismodegib and BCRP substrates are not expected.

Vismodegib capsules contain lactose monohydrate. Patients with the rare hereditary problems of galactose intolerance, primary hypolactasia, or glucose-galactose malabsorption should not take this medicine.

Because there is a potential for interaction of GDC-0449 with other concomitantly-administered drugs through the cytochrome P450 system, the case report form must capture the concurrent use of all other drugs, over-the-counter medications, or alternative therapies. The Principal Investigator should be alerted if the patient is taking any agent known to affect or with the potential to affect selected CYP450 isoenzymes.

- If plasma levels need to be lowered emergently, animal studies have suggested that oral administration of activated charcoal may lower drug plasma levels more quickly than drug cessation alone.
- Women of childbearing potential are required to have a negative serum pregnancy test (with a sensitivity of at least 25 mIU/mL) within 7 days prior to the first dose of GDC-0449 (serum or urine). A pregnancy test (serum or urine) will be administered every 4 weeks while on study within the 24-hour period prior to the administration of GDC-0449. Prior to dispensing GDC-0449, the investigator must confirm and document the patient's use of two contraceptive methods, dates of negative pregnancy test, and confirm the patient's understanding of the teratogenic potential of GDC-0449.

Female patients are required to use two forms of acceptable contraception (refer to [Appendix C](#)), including one barrier method during participation in the study and respectively for the 2 and 24 months following the last dose for both male and female patients. All patients should receive contraceptive counseling either by the investigator, or by an obstetrician (OB)/gynecologist or other physician who is qualified in this area of expertise. If a woman of childbearing potential believes that her contraceptive method has failed, emergency contraception should be considered. If a patient is suspected to be pregnant, GDC-0449 should be immediately discontinued. In addition, a positive urine test must be confirmed by a serum pregnancy test. If it is confirmed that the patients is not pregnant, the patient may resume dosing with GDC-0449.

If a female patient becomes pregnant during therapy or within 24 months after the last dose of GDC-0449, or if the female partner of a male patient exposed to the drug becomes pregnant while the male patient is receiving GDC-0449 or within 2 months after the last dose of GDC-0449, the investigator must be notified in order to facilitate outcome follow-up.

Abortion, whether accidental, therapeutic, or spontaneous, should always be classified as serious. Any congenital anomaly/birth defect in a child conceived during the study or within 24 months after the last dose of GDC-0449 to a female patient or to a female partner of a male patient

exposed to the agent during treatment or within 2 months after the last dose of GDC-0449 should be recorded and reported as an SAE.

- Female patients should not breastfeed a baby while on this study.
- Female patients must NEVER donate ova while being treated with GDC-0449.
- All sexually active male subjects (including those who have undergone vasectomy) should utilize a barrier form of contraception during study treatment and for 2 months after the last dose as it is not known whether GDC-0449 that may be present in seminal fluid would cause teratogenic effects in a fetus born to the female partner of a male subject. Males should also not donate sperm during treatment or up to 2 months after the last dose.
- All patients are prohibited from donating blood for 24 months after the last dose of GDC-0449.

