8.1 GDC-0449

| | | |
|-----------------------------|--|--------------------------|
| Chemical Name: | 2-chloro- N -[4-chloro-3-pyridin-2-yl-phenyl]-4-methanesulfonyl-benzamide | |
| Other Names: | Systemic Hedgehog Pathway Antagonist, G-025897, G-025897.1, and GDC-0449.1 | |
| Classification: | Hedgehog Pathway Antagonist | |
| CAS Registry Number: | 879085-55-9 | |
| Molecular Formula: | C ₁₉ H ₁₄ Cl ₂ N ₂ O ₃ S | M.W.: 421.3 g/mol |
| Mode of Action: | GDC-0449 provides anticancer responses by inhibiting the Hedgehog pathway. The Hedgehog signaling pathway controls cell differentiation, growth, and proliferation. It is most active during embryogenesis but may also play a role in the regulation of adult stem cells involved in the maintenance and regeneration of adult tissues. | |
| How Supplied: | GDC-0449 is supplied by Genentech. It is available as 150-mg grey and pink, size 1 capsules containing microcrystalline cellulose, lactose monohydrate, sodium lauryl sulfate, povidone, talc, | |

sodium glycolate, and magnesium stearate. Capsules are packaged in 75-mL round, white, high-density polyethylene (HDPE) bottles and closed with 38/400 two-piece HDPE child-resistant caps. Each bottle contains 32 capsules.

Storage: GDC-0449 should be stored at room temperature between 59°F and 86°F (15°C and 30°C) and should be protected from excessive exposure to light.

Stability: Stability testing is ongoing.

Route of Administration: Oral

Drug Administration: Patients should take GDC-0449 at approximately the same time each day, with or without food. If a patient misses a dose (e.g., due to emesis), he or she should be instructed not to take or make up that dose and to resume dosing with the next scheduled dose. Missed doses should not be made up.

Patient Care Implications: The terminal half-life of GDC-0449 is approximately 10-14 days in healthy volunteers. If plasma levels of GDC-0449 need to be lowered emergently, animal studies suggest that oral administration of activated charcoal may lower drug plasma levels more quickly than dose cessation alone.

Drug Interactions: Caution should be exercised when dosing GDC-0449 with narrow therapeutic con-meds that are metabolized by CYP2Cs. Warfarin falls into this category (CYP2C9 substrate, narrow TI).

Availability

GDC-0449 is an investigational agent supplied to investigators by Almac Clinical Services .

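### Section 5.2.1 ends the ova donation ban with treatment, while the sperm and blood donation bans in the same list run 2 and 24 months past the last dose

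*Combined protocol and SAP*

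**What the plan says.** The rules sit in Section 5.2.1, in the text on contraception and the short list that follows it.

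- **Ova:** "Female patients must NEVER donate ova while being treated with GDC-0449". No period after treatment is given. The capitalised adverb does not lengthen the ban, because the clause after it confines the rule to the time on treatment.
- **Sperm:** "Males should also not donate sperm during treatment or up to 2 months after the last dose".
- **Blood:** all patients are barred from donating for 24 months after the last dose.

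The same section sets long windows for women in other rules. Contraception applies "during participation in the study and respectively for the 2 and 24 months following the last dose for both male and female patients". The pregnancy notification rule begins "If a female patient becomes pregnant during therapy or within 24 months after the last dose of GDC-0449". Birth-defect reporting covers a "child conceived during the study or within 24 months after the last dose of GDC-0449 to a female patient".

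Section 7.1 repeats the sperm restriction but has no ova counterpart. Appendix C defines childbearing potential and acceptable contraception and does not deal with donation. On persistence, Section 8.1 states: "The terminal half-life of GDC-0449 is approximately 10-14 days in healthy volunteers".

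**The concern.** A ban during treatment shows that the authors accepted a precaution for donated ova. That precaution stops on the last day of dosing, when drug is still in the body. The neighbouring donation rules do not stop there, and nothing in the protocol explains why ova should be treated differently.

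The women's contraception window does not close the gap. It prevents pregnancy in the patient herself; it does not prevent her from donating ova to someone else. The person who might be exposed is therefore a third party, the embryo from a donated ovum, and no other rule covers that route. Section 7.1 describes the drug class as able to cause severe and irreversible malformations, which is why the other rules were written with long margins.

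**Working it through.** There is no planned figure to reproduce. The check is a comparison of the rules, followed by a short calculation on drug persistence.

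**Step 1. The three donation rules in Section 5.2.1**

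| Donated material | Who | Months barred after last dose |
|---|---|---|
| Ova | Women | 0 (none stated) |
| Sperm | Men | 2 |
| Blood | All patients | 24 |

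For a woman, the gap between the blood rule and the ova rule is 24 − 0 = 24 months.

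**Step 2. The windows for women elsewhere**

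Sections 3.1.10, 5.2.1 and 7.1 use 24 months. The safety text in Section 2.2, most of Section 7.3.4, and Appendix C use 12 months. One reporting trigger in Section 7.3.4 that names female patients uses 3 months. The ova ban covers 0 of 24, 0 of 12 or 0 of 3 months, so the gap is present whichever text governs.

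**Step 3. Is drug still present when the ban ends?**

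Input: half-life h of 10 to 14 days (Section 8.1, healthy volunteers). Assuming first-order decline, the fraction left t days after the last dose is 2^(−t/h).

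- t = 1 day: 2^(−0.1) = 93%; 2^(−1/14) = 95%.
- t = 28 days: 2^(−2.8) = 14%; 2^(−2) = 25%.
- t = 60 days: 2^(−6) = 1.6%; 2^(−60/14) = 5.1%.
- Time to 1%: h × log2(100) = 66 days (h = 10) and 93 days (h = 14).

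**Step 4. Can these percentages be trusted in patients?**

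Not closely. Section 2.2 reports, for 33 patients with basal-cell carcinoma, a median time to steady state of 14 days (interquartile range 7 to 22). The median steady-state level was 19.8 µM at 150 mg and 15.9 µM at 270 mg. Under linear kinetics with h = 10 to 14 days:

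- Share of steady state reached by day 14: 1 − 2^(−1.4) = 62%; 1 − 2^(−1) = 50%.
- Time to 90% of steady state: h × log2(10) = 33 days (h = 10) and 47 days (h = 14).

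Both results disagree with a 14-day median, and a higher dose that gives no higher level argues against simple linearity.

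As a sensitivity check, suppose that 14 days marks 90% of steady state and that elimination mirrors accumulation (both are assumptions). The effective half-life is then 14 / log2(10) = 4.2 days, and the fraction left is 0.1^(t/14): 85% at day 1 and 1% at day 28.

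Across both sets of assumptions, 85% to 95% remains one day after the last dose and 1% to 25% at day 28. The common result is that drug is still present when the ban ends. The later percentages are not firm.

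**The case against.** The strongest case against the point is that it is a trivial wording matter.

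- **Reach.** Patients enter with progressing metastatic or unresectable disease (Sections 3.1.8 and 3.1.9). Section 13.2 cites median survival of 7 to 17 months in metastatic disease, and progression ends treatment (Section 5.3). Ova donation afterwards is scarcely plausible. This stands as a limit on size. It does not make the number zero: mesenchymal chondrosarcoma is eligible, and Section 2.1 gives a median age at diagnosis of 25 years for it.
- **No documented harm.** The teratogenic concern is exposure of a developing embryo. The documents give no data on drug in ova, and Section 2.2 reports no evidence of genotoxicity. Section 7.3.4 calls the drug potentially genotoxic but adds no data. This stands. However, Section 5.2.1 imposes the male barrier rule because the effect of drug in seminal fluid is unknown, so the protocol already acts on precaution.
- **The length of the remedy.** Linear elimination at the Section 8.1 half-life supports roughly 2 to 3 months (66 to 93 days to 1%), well short of 24. This stands as a reason to let the sponsor justify a shorter period. It does not justify giving none.

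A reader might also infer four stronger things, none of which the documents support.

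- *That the sperm ban covers the men's whole window.* It does so only under the 2-month texts. Section 2.2 asks men for 12 months of barrier contraception, and Section 7.3.4 uses 12 months for birth defects and abortions in their partners. Sperm is therefore 2 of 2 or 2 of 12 months.
- *That the protocol already sets 24 months for ova.* It sets 24 months for blood donation, not for ova.
- *That this is the only rule for women without a period after the last dose.* The breastfeeding rule ("Female patients should not breastfeed a baby while on this study") and pregnancy testing ("A pregnancy test (serum or urine) will be administered every 4 weeks while on study") have none either. Neither concerns donation.
- *That a stated percentage of drug remains at a given week in patients.* The Section 2.2 data do not allow that precision.

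**Conclusion.** The gap is real and small. Of the three donation rules in Section 5.2.1, only the ova rule lacks a period after the last dose, and following it as written permits donation while drug remains.

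The conclusion rests on the plain wording, on the contrast with the 2-month sperm and 24-month blood bans, and on a half-life long enough for drug to be present the next day. It does not depend on any particular residual percentage or on proof of harm through ova.

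The number of women who could donate among the 45 planned patients is not given and is likely very small. The consent pages were not available, so the patient information may already say more. The primary endpoint, the Simon design, the sample size and the analyses are untouched. This is a cheap precautionary improvement, not a threat to the trial's result.

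**What to change.** Amend the ova bullet in Section 5.2.1 so that donation is barred during treatment and for 24 months after the last dose. That period matches the blood ban in the same list and the women's contraception window in Sections 3.1.10, 5.2.1 and 7.1. If the sponsor prefers another period, state it with a reason. Check that the patient information carries the same rule.

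The cost is one clause and one document check. The downside is a longer restriction on the few women who might donate. Patient numbers, visits and analyses do not change.
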